## **5.8 Pharmacokinetic Evaluations**

No pharmacokinetic data were collected in this study.

## **6 SAFETY ANALYSIS**

Safety analyses will be conducted on the treated population. All safety and other data will be listed. Subjects who were re-randomized will be considered as two individual subjects for the safety analyses. If such a subject is treated at least once with rimegepant, then their treatment group assignment is rimegepant for all treated subject numbers pertaining to the same subject.

Safety outcome measures include: adverse events, laboratory assessments including liver toxicity, physical examinations, vital signs, physical measurements, ECGs, and concomitant medications.

Unless otherwise noted, baseline is considered as last assessment prior to study drug randomization.

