**Table 3: Estimands for the Exploratory Efficacy Objectives**

Objective	Functional Disability at 24 hours
Population	mITT
Variable	Percent of subjects with a response of “normal” at 24 hours post-dose
Intercurrent Events	NC=F; RM=F
Pop. Summary	Percentage within each treatment group (BHV3000 & Placebo)
Objectives	Pain Relief at 30, 60 or 90 minutes post-dose
Population	mITT
Variable	Percent of subjects who report pain as mild or none at the time point of interest
Intercurrent Events	NC=F; RM=F
Pop. Summary	Percentage within each treatment group (BHV3000 & Placebo)
Objectives	Preference of Medication
Population	Treated subjects who: 1) answer “yes” to the lead-in question (i.e. “Have you ever taken migraine medication?”) and provide preference of medication data
Variable	Percentage of subjects who prefer study medication to previous migraine medications
Intercurrent Events	Observed analysis. No accounting for intercurrent events.
Pop. Summary	Percentage within each treatment group (BHV3000 & Placebo)
Objectives	Pain Relief, on a 4 point scale, at all time points
Population	mITT
Variable	Percent of subjects who report pain as none, mild, moderate or severe
Intercurrent Events	NC=F; RM=F
Pop. Summary	Percentage of each response, in each treatment group (BHV3000 & Placebo)
Objectives	Migraine Quality of Life Questionnaire
Population	mITT
Variable	Total score on the MQoLQ
Intercurrent Events	Observed analysis. No accounting for intercurrent events.
Pop. Summary	Average total score within each treatment group (BHV3000 & Placebo)
Objective	Safety and Tolerability
Population	All treated subjects
Variables	Multiple
Intercurrent Events	Subjects analyzed as treated. No accounting for intercurrent events
Pop. Summary	Multiple (discussed under Section 6, “Safety Analyses”)
Objective	Sheehan Suicidality Tracking Scale
Population	All treated subjects
Variables	Change from baseline in the total score
Intercurrent Events	Subjects analyzed as treated. No accounting for intercurrent events
Pop. Summary	Percentage of subjects, by treatment group, in each of 5 categories (<-1, -1, no change, 1, >1)

CCI

CCI

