## **4 SUBJECT POPULATIONS**

### **4.1 Population Definitions**

The following subject populations will be evaluated and used for presentation and analysis of the data:

- Enrolled subjects: patients who sign an informed consent form and are assigned a subject identification number
- Randomized subjects: enrolled subjects who receive a randomization treatment assignment from the interactive web response system (IWRS), regardless of the treatment they actually received or subsequent withdrawal from treatment
- Treated subjects: enrolled subjects who take any amount of study therapy (rimegepant or placebo)
- Modified Intent-to-Treat (mITT) subjects: Randomized subjects who are randomized only once, take study medication, have a baseline migraine of moderate to severe intensity, and who provide at least one post-baseline efficacy data point. Subjects that re-enrolled in the study, and were randomized on two or more occasions are not included in the mITT population.

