**5.2.7 Re-Screened and Re-Randomized Subjects**

In the event a subject is re-screened, then the data from the last screening visit, and latest laboratory assessment are used for the screening data.

In the event a subject is re-randomized, the subject will not be analyzed as part of the mITT population for the efficacy analyses. For safety, all AEs that occurred after the date of randomization for the treated subjects will be considered on-study. If such a subject is treated at least once with BHV-3000 (rimegepant), then their treatment assignment is BHV-3000 (rimegepant) for all treated subject numbers pertaining to the same subject.

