## **6.2 Adverse Events**

Adverse events (AEs) will be coded using MedDRA and displayed in tables and listings by system organ class (SOC) and preferred term (PT).

Analyses of AEs will be performed for those events that are considered on-study AEs with a start date prior to 30 days after the last dose of study medication. On-study is defined as any AE that developed, worsened, or became serious after study randomization.

Adverse events are summarized by subject incidence rates; therefore, in any tabulation, a subject contributes only once to the count for a given AE (SOC or PT).

The number and percentage of subjects with any on-study AE, with any on-study AE related to treatment (definite, probable, or possible relationship), with any on-study SAE, with any on-study severe AE, and with any on-study AE leading to discontinuation will be summarized by treatment group and overall. In these tabulations, each subject will contribute only once (i.e., the most related occurrence or the most intense occurrence) to each of the incidence rates in the descriptive analysis, regardless of the number of episodes.

No formal hypothesis-testing of AE incidence rates will be performed.

All AEs occurring pre-randomization and on-study will be listed. Additional listings will be provided including: deaths; SAEs; and AEs leading to discontinuation.

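### For a re-randomised person treated once with each drug, the SAP tabulates the placebo dose and its adverse events as rimegepant, against its own as-treated principle

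*SAP*

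**What the plan says.** Two places in the SAP set the rule. Section 6 states that "Subjects who were re-randomized will be considered as two individual subjects for the safety analyses" and that, where at least one dose was rimegepant, "their treatment group assignment is rimegepant for all treated subject numbers pertaining to the same subject". Section 5.2.7 gives the same assignment ("then their treatment assignment is BHV-3000 (rimegepant) for all treated subject numbers pertaining to the same subject") and adds that "all AEs that occurred after the date of randomization for the treated subjects will be considered on-study". Neither makes an exception for the order of the two doses.

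Three other places bear on it. In SAP Table 3 the safety and tolerability entry reads "Subjects analyzed as treated. No accounting for intercurrent events". SAP 6.2 summarises adverse events by subject incidence, so that "in any tabulation, a subject contributes only once to the count for a given AE (SOC or PT"). Protocol 9.1 likewise says that tabulations of adverse events and laboratory abnormalities count unique subjects, with repeat occurrences of an event counted once.

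For efficacy, SAP 4.1 takes these people out: "Subjects that re-enrolled in the study, and were randomized on two or more occasions are not included in the mITT population".

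**The concern.** A placebo dose labelled rimegepant is not analysed as treated. If someone takes placebo under the first number, has an adverse event, and later takes rimegepant under a second number, the first event is tabulated under rimegepant although no rimegepant had been taken when it occurred. The rimegepant group gains a record that carries no rimegepant exposure, and the placebo group loses a treated record.

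Two things are at stake. Adverse event rates by treatment are blended slightly, which pulls the arms together. More importantly, a rare event can change arm. Protocol 1.3.4 names change in liver function tests as the primary identified adverse event of interest. SAP 6.3.1 presents liver outputs by treatment group, including a plot that is also produced for the combined 301/302 data. With outputs of that kind, the arm to which one case belongs matters.

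**Working it through.** **Base.** Protocol 9.2 and SAP 5.1 expect about 90% of 600 randomised per arm to be treated, and state approximately 550 per group. The product is 0.90 × 600 = 540, which agrees with the stated 550 to within 2% (10/550 = 1.8%). The stated 550 is used below.

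**Who is affected.** The rule acts on treated subject numbers.

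- Re-randomised but treated only once: no placebo dose is relabelled.
- Treated twice with the same drug: nothing is relabelled, but one person counts as two.
- Treated once with each drug, in either order: the placebo record becomes a rimegepant record.

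Let k be the number of people in the last group. The documents give no value for k, so a range is shown.

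**Assumptions.** There are 550 rimegepant doses and 550 placebo doses, with k of each coming from people who took both. The adverse event risk per dose is pR on rimegepant and pP on placebo, and is the same for re-randomised people as for others. The rates 15% and 10% are illustrative and are not taken from the documents.

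**Formulae under the SAP rule.**

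- Rimegepant denominator: 550 + k. Placebo denominator: 550 − k.
- Expected rimegepant rate: (550·pR + k·pP)/(550 + k). The expected placebo rate stays at pP.
- Expected difference: (550·pR + k·pP)/(550 + k) − pP = (pR − pP) × 550/(550 + k).

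The difference shrinks toward zero whatever its sign.

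**Numbers, pR = 15% and pP = 10% (true difference 5.00 points).**

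| k | Denominators (rimegepant / placebo) | Factor 550/(550+k) | Rimegepant rate | Difference |
|---|---|---|---|---|
| 1 | 551 / 549 | 0.998 | 14.99% | 4.99 |
| 5 | 555 / 545 | 0.991 | 14.95% | 4.95 |
| 10 | 560 / 540 | 0.982 | 14.91% | 4.91 |
| 20 | 570 / 530 | 0.965 | 14.82% | 4.82 |

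For k=10: (82.5 + 1.0)/560 = 14.91%, less 10% = 4.91 points.

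**One rare event after a placebo dose, k=1.** By dose taken: rimegepant 0/550, placebo 1/550 (0.182%). Under the SAP rule: rimegepant 1/551 (0.181%), placebo 0/549.

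**If each treated number follows the drug taken under it,** the denominators stay at 550 and 550, the expected difference is 5.00 points, and the rare event stays with placebo.

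**The case against.** The strongest defence is that the rule is deliberate. It appears twice in consistent terms and is an ever-exposed convention that charges doubtful events to the active drug. Table 3 refers its safety summary to section 6, so section 6 could be read as defining what as-treated means in a case that the table does not address. Likewise, the once-per-subject count is formally kept if subject means subject number.

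Part of this stands. The rule is conservative for an individual event. It is not conservative for rates, because the placebo record enters the rimegepant denominator too and dilutes a true excess. Reading subject as subject number does not meet the reference to unique subjects in protocol 9.1. If an exception to as-treated was intended, Table 3 does not say so.

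The points on scale stand in full. The protocol plans one dose per patient and describes no re-randomisation, so the case should be exceptional. Adverse event rates are not formally tested. SAP 6 and 6.2 list all safety data and all adverse events, and SAP 6.1 lists exposure and accountability for every randomised subject, so a careful reader could trace a misplaced event. No separate listing of re-randomised subjects is specified, however.

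A reader might infer more than the documents support:

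- That exposure counts, or every safety table, are wrong. The exposure and accountability tables in SAP Appendix 1 use all randomised subjects, and their cross-tabulation is overall only. The SAP does not say that the rule for treated numbers governs them.
- That efficacy is affected. These people are outside the mITT set. Protocol 9.3 is silent on re-randomisation where SAP 4.1 excludes such subjects. That is a separate difference in wording, and no effect on results has been shown.
- That every re-randomised person is misattributed. Only those treated with both drugs are.

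**Conclusion.** The point holds, and it is minor. As written, SAP 5.2.7 and 6 place a placebo-dose record and its adverse events under rimegepant for anyone treated once with each drug, which conflicts with Table 3. Counting one person as two conflicts with SAP 6.2 and protocol 9.1.

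For common adverse events the distortion is under 0.1 point at k=10 with the assumed 15% and 10%, and about 0.01 point at k=1. The consequence worth preventing is a single serious or liver event shown in the wrong arm, for which k=1 is enough. These sizes rest on an assumed 550 doses per arm, illustrative event rates, and a k that the documents do not report. If k is zero, no record is relabelled and only the wording needs repair.

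**What to change.** In SAP 5.2.7 and 6, replace the assignment rule for the by-treatment safety tables of treated subjects: each treated subject number belongs to the drug actually taken under that number. Then:

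- Reconcile Table 3, 5.2.7, 6 and 6.2 so that they state one principle. Say whether the counting unit for re-randomised people is the person or the treated number, including in the overall column and for same-drug repeats. Section 6 speaks of two subjects while 4.1 allows two or more randomisations, so the wording should cover a third.
- Report the number of re-randomised subjects, and list them with the drug taken under each number.
- If the ever-rimegepant allocation is wanted as a cautious view, keep it as a labelled sensitivity table.

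Counting the person once and attributing each event to the last drug taken is a tempting alternative, but it is incomplete. It leaves open which arm's denominator holds the person. Because on-study events start at randomisation, an event before the first dose would also have no drug to attach to.

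The cost is a few lines of SAP text, a small change to one derivation and one short listing. No new data are needed.

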### **6.1 Extent of Exposure**

Extent of exposure is measured by subjects providing self-reported drug exposure information in their eDiaries. As a check on this exposure data, drug accountability data are provided by the study center on the “Drug Accountability” CRF page.

The self-reported exposure data will be tabulated by treatment group, and will include:

- The number (and percentage) of randomized subjects that took study medication
  - The number and percentage who took the medication prior to providing baseline study migraine characteristics
  - The number and percentage that took study medication after providing baseline study migraine characteristics
- The number and percentage of randomized subjects who reported not taking study medication

- The number and percentage of randomized subjects for whom no exposure data was reported

The drug accountability will be tabulated by treatment and overall, and will include:

- The number and percentage of randomized subjects to whom kits were dispensed
- The number and percentage of kits returned
  - The number and percentage of kits returned from which the IP was used
  - The number and percentage of kits returned from which the IP was not used
- The number and percentage of kits not returned

A cross tabulation of exposure and accountability data will be prepared. This will be done overall. For the exposure data the categories are: Took IP, Did not Take IP, and Unknown. For the accountability data, the categories will be: IP Used, IP not Used, and Unknown.

A listing will be prepared that indicates the exposure and accountability status of all randomized subjects. A patient identifier (PID) listing will be prepared if subjects had unknown exposure data, unknown accountability data, or for whom the exposure and accountability data did not match.

## **6.2 Adverse Events**

Adverse events (AEs) will be coded using MedDRA and displayed in tables and listings by system organ class (SOC) and preferred term (PT).

Analyses of AEs will be performed for those events that are considered on-study AEs with a start date prior to 30 days after the last dose of study medication. On-study is defined as any AE that developed, worsened, or became serious after study randomization.

Adverse events are summarized by subject incidence rates; therefore, in any tabulation, a subject contributes only once to the count for a given AE (SOC or PT).

The number and percentage of subjects with any on-study AE, with any on-study AE related to treatment (definite, probable, or possible relationship), with any on-study SAE, with any on-study severe AE, and with any on-study AE leading to discontinuation will be summarized by treatment group and overall. In these tabulations, each subject will contribute only once (i.e., the most related occurrence or the most intense occurrence) to each of the incidence rates in the descriptive analysis, regardless of the number of episodes.

No formal hypothesis-testing of AE incidence rates will be performed.

All AEs occurring pre-randomization and on-study will be listed. Additional listings will be provided including: deaths; SAEs; and AEs leading to discontinuation.

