8.2.1 Collection and Reporting of Non-Serious Adverse Events

The collection of non-serious AE information should begin at the Baseline visit. Non-serious AE information should also be collected from any observational period intended to establish a baseline status for a patient.

Non-serious adverse events should be followed until conclusion or stabilization, or reported as SAEs if they become serious. Follow-up is also required for non-serious AEs that cause interruption or discontinuation of study drug or those that are present at the end of study treatment.

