## **2 STUDY DESIGN**

### **2.1 Synopsis of Study Design**

BHV3000-302 is a Phase III, multicenter, randomized, double-blind, 2-arm placebo-controlled parallel-group study designed to assess safety and efficacy in the treatment of moderate to severe migraine.

After providing informed consent, subjects will first participate in the screening phase (3-28 day period) to determine eligibility for the study.

[figure not shown]
After randomization, the subject will be dispensed a single dose of the double-blind study medication to take home for up to 45 days. This study medication is to be taken when a migraine attack reaches moderate or severe intensity on the numeric rating scale (NRS) as indicated in the electronic diary (eDiary). The subject will complete an eDiary for up to 48 hours after taking the study medication. Subjects will record efficacy data in their eDiary and will telephone the study center immediately if a severe or serious adverse event occurs.

Subjects will return to the study site within 7 days of study treatment for review of the eDiary, assessment of medication compliance, and monitoring of tolerability and safety. If a subject has NOT experienced a migraine headache of sufficient severity within the 45 days after randomization, he or she will be withdrawn from the trial.

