### **5.2.8 Missing and Partial Dates**

For efficacy analyses, partial or missing dates will not be imputed. The relative study days, where determined, will be calculated for full dates only.

For rescue medication, if the time of rescue medication is missing, then all endpoints on or after the date of rescue medication will be imputed as failures.

For missing and/or partial dates regarding concomitant/prior medications, a conservative approach will be taken. The medication will be assumed to be concomitant if it cannot be definitively shown that the medication was not taken after the period beginning 14 days prior to the taking of study medication.

If the start date of an AE is partially or completely missing, then the date will be compared as far as possible with the date of the randomization. The AE will be assumed to be on-study if it cannot be definitively shown that the AE did not occur or worsen during the post-randomization period (worst case approach).

The following general rules will be used:

- If the start day is missing, but the start month and year are complete, an AE will only be excluded as being on-study if the start month/year is before the month/year of randomization or if the stop date is before randomization.
- If the start day and month are missing, but the start year is complete, an AE will only be excluded as being on-study if start year is before the year of randomization or if the stop date is before randomization.
- If the start date is completely missing, an AE will be considered on-study unless the stop date is before randomization.

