### 6.3 Laboratory Data

Clinical laboratory evaluations include:

- Hematology: hemoglobin, hematocrit, red blood cell count, white blood cell count with differential, and platelets
- Serum Chemistry: sodium, potassium, chloride, bicarbonate, calcium, glucose, BUN (urea), serum creatinine, uric acid, ALT, AST, alkaline phosphatase, LDH, total protein, albumin, total bilirubin, direct bilirubin, indirect bilirubin, CPK (with fractionation, if available)
- Lipid Panel: Cholesterol, LDL, HDL, triglycerides (screening only)
- Estimated glomerular filtration rate (eGFR) using the estimated MDRD formula will be calculated and reported by the central lab at each visit that the clinical laboratory test is collected.
- Urinalysis: pH, specific gravity, protein, ketones, nitrites, urobilinogen, leukocyte esterase, protein, glucose, microalbuminuria, and blood. If blood, protein, or leukocytes are positive, reflex to microscopic examination.
- Urine drug screen: for drugs of abuse

Clinical laboratory values will be expressed using both Standard US units and SI units. Tabulations, listings, and graphics will be provided to show the data in both systems. The observed value and change from baseline will be summarized for select continuous laboratory parameters. In addition, shift tables (low, normal, high) will be presented. For AST and ALT, the shift tables will use the categories: Normal, >ULN, >3x ULN, and >5x ULN. In the event of repeat values from the same visit, the non-missing value closest to the target date for the visit will be used. In the case of a tie, the latest record will be used.

All laboratory data will be provided in data listings. Additional listings will be presented for all abnormal laboratory values.

On-study laboratory abnormalities are those with an assessment date after the date/time of first dose of study drug and within 30 days after the last dose of study drug.

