#### 6.3.1 *Liver Toxicity Evaluation*

Potential drug induced liver injury are those events meeting Hy's Law, defined as:

1. Aminotransferases (AT) ALT or AST elevation > 3 times the upper limit of normal (ULN);
2. Total bilirubin (TBL) > 2 times ULN, without initial findings of cholestasis (elevated serum alkaline phosphatase); and

3. No other immediately apparent possible causes of AT elevation and hyperbilirubinemia, included but not limited to: viral hepatitis, pre-existing chronic or acute liver disease, or the administration of other drug(s) known to be hepatotoxic.

Any potential drug-induced liver injuries (DILIs), meeting the above defined criteria, will be reported as SAEs and tabulated by treatment group. A listing will be prepared that shows the AT and TBL values for all subjects that experience either AT > 3 times the upper limit of normal or TBL > 2 times the upper limit of normal at any time during the study.

Additionally, a table will be created that summarizes the incidence (as the number of subjects experiencing the given measurement post-randomization) of the following:

- >3x, >5x, >10x, and >20x ULN elevations of AST, ALT, and either ALT or AST
- Any elevations of bilirubin >1x ULN and >2x ULN
- Any elevations of ALP > 1.5x ULN
- Elevation of AST or ALT (>3x ULN) accompanied by elevated bilirubin (>1.5x ULN and >2x ULN)
- Elevation of AST or ALT along with an on-study AE of nausea, vomiting, anorexia, abdominal pain, or fatigue

An evaluation of Drug-Induced Serious Hepatotoxicity (eDISH) plot will be created by plotting the maximum total bilirubin against maximum ALT and presenting these data points by treatment group for the current study and the BHV3000-301/302 meta-analysis. The maximum values for each subject during the study will be identified as the maximum values that occur post-baseline, but not necessarily concurrently. Maximum total bilirubin (presented as xULN) will be plotted on a log scale on the y-axis and maximum ALT (presented as xULN) will be plotted on a log scale on the x-axis. A horizontal reference line will be placed at 2x ULN for maximum total bilirubin and a vertical reference line will be placed at 3x ULN for maximum ALT. The lower left quadrant will be labeled “Normal Range”. The upper left quadrant will be labeled “Hyperbilirubinemia”. The lower right quadrant will be labeled “Temple’s Corollary”. The upper right quadrant will be labeled “Possible Hy’s Law Range”.

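### AE tables in treated subjects count on-study events from randomization, up to 45 days before the single dose, while the laboratory section starts on-study at the dose

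*SAP*

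**What the plan says.** Safety analyses use treated subjects (SAP section 6). Under SAP section 2.1 each subject is "dispensed a single dose of the double-blind study medication to take home for up to 45 days", and protocol section 7.2.2 gives the same 45-day limit. Non-serious events are already being gathered during that wait: "The collection of non-serious AE information should begin at the Baseline visit" (protocol section 8.2.1).

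The starting points differ by section:

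- SAP 6.2, adverse events: "On-study is defined as any AE that developed, worsened, or became serious after study randomization". The start date must also fall before 30 days after the last dose.
- SAP 5.2.7, re-randomized subjects: "all AEs that occurred after the date of randomization for the treated subjects will be considered on-study".
- SAP 5.2.8, incomplete dates: an AE counts as on-study unless it can be shown that it "did not occur or worsen during the post-randomization period".
- SAP 6.3, laboratory data: "On-study laboratory abnormalities are those with an assessment date after the date/time of first dose of study drug", up to 30 days after the last dose.
- SAP 6.3.1, liver table: incidence is "the number of subjects experiencing the given measurement post-randomization". One row is "Elevation of AST or ALT along with an on-study AE of nausea, vomiting, anorexia, abdominal pain, or fatigue".

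Tables 14.3.2.1 to 14.3.2.6 (SAP Appendices 1 and 5) are all on-study AE tables in treated subjects. The two AE timing listings, 16.2.9.1 and 16.2.9.2, divide events only at randomization.

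**The concern.** In a single-dose trial, the AE percentage a reader quotes is taken to mean the share of subjects with an event after taking the tablet. The planned tables do not give that. They add events from a drug-free wait of up to 45 days and label them with the randomized arm. Protocol section 8 itself ties an AE to the time of product use.

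The same term also carries two starting points within one SAP, and they meet in liver table 14.4.7, which is titled as on-study. Nausea or fatigue weeks before the dose could be paired there with an enzyme rise found after it. Protocol section 1.3.4 names liver tests as the main AE of interest, so this table needs one unambiguous window.

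**Working it through.** **Length of the pre-dose window.** Protocol section 4.1 puts the study at about 11 weeks. Screening 28 + acute phase 45 + follow-up 7 = 80 days, and 80/7 = 11.4 weeks, so the stated duration includes the full 45 days before dosing. At that maximum, the pre-dose part is 45/(45+7) = 87% of the time from randomization to a day-7 visit, and 45/(45+30) = 60% of the time to the 30-day AE cut-off. Most subjects will wait less.

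**Wait to dose (illustration).** Assume memoryless attacks and that the first qualifying attack is treated. The daily rate r comes from:

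- the eligibility limits in protocol section 5.2: 8/30 = 0.2667 and 2/30 = 0.0667;
- the 90% with a migraine in the allotted period in protocol section 9.2: −ln(0.10)/45 = 0.0512.

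Mean wait given dosing within 45 days: W = 1/r − 45·exp(−45r)/(1 − exp(−45r)) = 3.75, 12.6 and 14.5 days.

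**Chance of a pre-dose AE.** Assumed post-dose rates are 10% (rimegepant) and 5% (placebo). The pre-dose hazard is h = k·(−ln 0.95)/F per day. F is the days observed after the dose: 7 (planned visit), 21 (upper end of the End of Treatment interval in SAP Table 6) or 30 (AE cut-off). The factor k is 1 for a hazard equal to placebo after the dose, or 0.5 for half of it. Averaging over the truncated exponential wait:

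q = 1 − [r/(r+h)]·[1 − exp(−45(r+h))]/[1 − exp(−45r)]

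Tabulated rate = 1 − (1 − post)(1 − q). Pre-dose share of background AEs = kW/(kW + F).

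Worked case, 2 attacks per month, F = 7, k = 1: h = 0.0513/7 = 0.00733, and q = 1 − 0.90097 × 0.96420/0.95021 = 1 − 0.91424 = 8.6%. Rimegepant: 1 − 0.90 × 0.91424 = 17.7%. Placebo: 1 − 0.95 × 0.91424 = 13.1%.

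All cases, as tabulated rimegepant vs placebo, with the pre-dose share of background AEs in brackets:

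| Days observed, k | 8 per month | 2 per month | 90% in 45 days |
|---|---|---|---|
| 7, k = 1 | 12.4% vs 7.5% (35%) | 17.7% vs 13.1% (64%) | 18.8% vs 14.3% (68%) |
| 7, k = 0.5 | 11.2% vs 6.3% (21%) | 14.0% vs 9.2% (47%) | 14.6% vs 9.9% (51%) |
| 21, k = 1 | 10.8% vs 5.9% (15%) | 12.7% vs 7.9% (38%) | 13.1% vs 8.3% (41%) |
| 30, k = 1 | 10.6% vs 5.6% (11%) | 11.9% vs 7.0% (30%) | 12.2% vs 7.3% (33%) |

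The true difference of 5.0 points becomes 4.5 to 4.9 in the first row, 4.7 to 4.9 in the second, and 4.8 to 5.0 in the last two. The true ratio of 2.0 falls to between 1.65 and 1.32 in the first row.

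**What is barely touched.** Laboratory tests, ECG and physical examination are scheduled only at Screening and End of Treatment (protocol Table 1), so few such results fall between randomization and dose. In the liver table, mainly the AE-symptom row can change. Table 14.3.2.3 (related AEs) is partly filtered by the investigator's causality judgement.

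**The case against.** The strongest reply is that little depends on this. No AE rates are tested, pre-dose events balance across arms on average, the absolute difference moves by half a point or less in these illustrations, and the SAP computes no risk ratio. That is right, and it limits the harm to the percentages reported and the relative impression they give.

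The size is also open to challenge. The 14.5-day wait implies 0.0512 × 30 = 1.54 attacks per month, below the eligibility minimum of 2, and SAP section 5.1 reads the 90% as having a migraine treated with study drug, so other reasons for not dosing may be included. Without that case the top share falls from 68% to 64% and the worst pair becomes 17.7% vs 13.1%. Even this puts every subject at the minimum frequency. Equal hazard is probably on the high side too: the post-dose period contains the treated attack and possible rescue medication, and with no visit scheduled between Baseline and the attack, mild pre-dose events may be under-recalled. The half-hazard row shows the smaller effect.

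It can also be said that each section states its own rule and can be programmed, and that counting from randomization is cautious. Each rule can be programmed, but the on-study label does not tell the reader which window applies. Caution does not follow either: the rule raises both rates and makes the arms look more alike in relative terms. Subject listings are no substitute, because the SAP does not say that onset will be shown against dose time, and a listing does not correct a tabulated rate.

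**Conclusion.** The concern holds. The randomization anchor is explicit and appears in three SAP sections, it differs from the dose anchor for laboratory abnormalities, and no planned table reports AE incidence after the dose. The direction is certain: higher AE percentages in both arms and a diluted relative contrast, with no systematic bias between arms. The size is not known from the documents. The figures rest on assumed post-dose rates of 10% and 5%, memoryless attacks, treatment of the first qualifying attack and an assumed pre-dose hazard. Within those assumptions the inflation runs from about 0.6 points per arm (30 days observed, frequent attacks) to about 9 points (7 days observed, longest wait). This should be corrected, but it does not threaten the efficacy conclusions.

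**What to change.** - Define the AE incidence tables by onset or worsening on or after the date and time of study drug intake, and use that definition in SAP 6.2, 6.3 and 6.3.1.
- Use the dose date in the partial-date rules of SAP 5.2.8, and align 5.2.7.
- Show AEs after randomization but before the dose, in treated subjects, in their own table or listing. The randomization-anchored table can stay as supplementary.
- Count an event as post-dose when its order relative to dosing cannot be established. This covers dose-day events without a start time, and subjects whose dose time is missing or whose eDiary and accountability records conflict, which SAP 6.1 anticipates.

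A separate minor point on the same tables: the exploratory safety objective refers to AEs of at least moderate intensity, and protocol section 9.4.3 promises AEs by intensity, yet the SAP table list cuts only at severe. Add a table by maximum intensity with a moderate-or-severe row.

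The cost is SAP wording, one derived flag, a tie rule and a few tables. Dose date and time are already to be entered in the eDiary (protocol section 4.3.2), so no new data collection is needed.
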